10.4.4 Supportive and sensitivity analyses

Parts 1 & 2: Safety run-in and biomarker cohort

Not applicable.

Part 3: Double-blind, randomized, placebo-controlled part

As a supportive analysis, PFS based on RECIST 1.1 criteria as per blinded independent central review will be analyzed using a stratified Cox model, with the same analysis conventions as the primary efficacy analysis (based on investigator assessment), and the treatment effect will be summarized by the hazard ratio with its 95% confidence interval. Kaplan-Meier curves, quartiles and associated 95% confidence intervals will be presented for each treatment group.

Similarly, the above analysis will be performed for PFS based on tumor response criteria based on guidelines for immunotherapy as per blinded independent central review.

As sensitivity analyses for PFS and OS in the FAS, the hazard ratio and 95% confidence interval will be obtained from:

- An unstratified and covariate unadjusted Cox model
- A stratified and covariate adjusted Cox model that may include the following covariates: gender, age group (< 65, ≥ 65 years), LDH group (< 1 x ULN, ≥1 to < 2 x ULN, ≥ 2 x ULN), ECOG PS (0, 1, 2), sites of disease at baseline (< 3, ≥ 3), stage at screening (IIC or IVM1a vs IVM1b or IVM1c), BRAF mutation (V600E, V600K), and prior adjuvant checkpoint inhibitor therapy (yes, no). A final list of covariates of interest will be defined in the SAP.

- PFS and OS will also be analyzed based on the PPS, using the same analysis conventions as in the primary efficacy analysis (with the exception of the log-rank test, which will not be performed).

If the primary PFS analysis is statistically significant, subgroup analyses to assess the homogeneity of the treatment effect across demographic and baseline disease characteristics will be performed. The following subgroups may be considered: gender (male, female), age group (< 65, ≥ 65 years), LDH group (< 1 x ULN, ≥1 to < 2 x ULN, ≥ 2 x ULN), ECOG PS (0, 1, 2), sites of disease at baseline (<3, ≥ 3), stage at screening (IIC or IVM1a vs IVM1b or IVM1c), BRAF mutation (V600E, V600K), and prior adjuvant checkpoint inhibitor therapy (yes, no). An additional subgroup will be derived for those who experienced at least 1 immune-related AE (yes, no). A final list of subgroups of interest will be defined in the SAP.

The number of subjects censored for PFS and OS and reasons for censoring will be summarized by treatment group using descriptive statistics.

Additional key supportive analyses for PFS and OS will be performed to take into account delayed treatment effect leading to non-proportional hazards. Due to the expected non-proportional hazards the treatment effect will be estimated by means of a restricted mean survival time (RMST) approach (Uno et al., 2014).

The RMST and 95% CIs will be estimated for each treatment group separately and the treatment effect will be derived as the difference in the treatment group RMSTs with the 95% CI for the difference also being provided. Additional supportive analyses will include methods that provide alternative tests and treatment effect estimates in the presence of non-proportional hazards, e.g. weighted log-rank test with Fleming-Harrington class of weight (Fleming & Harrington, 1991), landmark analyses, piece-wise Cox regression to obtain HR by period. Details of all these analyses will be outlined in the SAP.

Additional supportive [REDACTED] analyses may be conducted to support the primary objective of the safety run-in, biomarker cohort, or randomized part, if appropriate, and the details of these analyses will be defined in the SAP.

10.5 Secondary objectives

[figure not shown]
Part 1: Safety run- in and Part 2: Biomarker cohort

The secondary objectives for these parts of the study are to determine the safety and tolerability, evaluate preliminary anti-tumor activity, characterize the pharmacokinetics, and evaluate the prevalence and incidence of immunogenicity of PDR001 in combination with dabrafenib and trametinib.

Part 3: Double-blind, randomized, placebo-controlled part

The secondary objectives in this part of the study are to compare the two treatment groups with respect to OS, tumor related efficacy variables (ORR, DOR, and DCR based on RECIST 1.1), safety and tolerability, quality of life, pharmacokinetics, and immunogenicity.

OS is identified as the key secondary endpoint. A hierarchical testing strategy will be used to control the overall type I error rate, where OS will only be formally tested and interpreted if the primary analysis of PFS is statistically significant.

10.5.1 Key secondary objectives

Part 1: Safety run-in and Part 2: Biomarker cohort

Not applicable.

Part 3: Double-blind, randomized, placebo-controlled part

The key secondary objective is to determine whether treatment with PDR001 in combination with dabrafenib and trametinib prolongs OS compared with dabrafenib and trametinib plus placebo. OS is defined as the time from date of randomization to date of death due to any cause. If a patient is not known to have died, then OS will be censored at the latest date the patient was known to be alive (on or before the cut-off date).

The following statistical hypotheses will be tested to address the key secondary efficacy objective for OS:

$$H_{02} : \theta_2 \geq 1 \text{ vs. } H_{12} : \theta_2 < 1$$

where θ_2 is the OS hazard ratio (PDR001 combined with dabrafenib and trametinib versus dabrafenib and trametinib plus placebo). The analysis to test these hypotheses and compare the two treatment groups will consist of a stratified log-rank test at an overall one-sided 2.5% level of significance. The stratification will be based on the randomization stratification factors, i.e., (LDH level: $< 1 \times \text{ULN}$ vs ≥ 1 to $< 2 \times \text{ULN}$ vs $\geq 2 \times \text{ULN}$; ECOG PS: 0 vs 1 vs 2).

OS analyses will be conducted as a part of a three-look group sequential design using a Lan-DeMets (O'Brien-Fleming) alpha spending function. Analyses will be based on the FAS population according to the randomized treatment group and strata assigned at randomization. The OS distribution will be estimated using the Kaplan-Meier method, and Kaplan-Meier curves, quartiles and associated 95% confidence intervals will be presented for each treatment group. The hazard ratio for OS will be calculated, along with its 95% confidence interval, using a stratified Cox model.

OS data will be presented at each analysis but will be formally tested hierarchically as follows:

If PFS is statistically significant at the interim PFS analysis:

Interim OS data will be tested at the time of the interim and final PFS analyses.

A final (inferential) analysis for OS is planned when approximately 245 deaths have occurred (or earlier if specifically requested by health authorities).

If PFS is not statistically significant at the interim PFS analysis:

Interim OS data will not be tested at the time of the interim PFS analysis.

If PFS is statistically significant at the final PFS analysis:

Interim OS data will be tested at the time of the final PFS analysis. If OS is not statistically significant at this stage, a final OS analysis will be planned after approximately 245 deaths.

If PFS is not statistically significant at the final PFS analysis:

Interim OS data will not be tested and there will also not be testing of OS data at the planned final OS analysis.

In the case of statistically significant interim or final OS results, additional OS estimates at relevant annual milestones up to 5 years will be summarized.

Following final PFS analysis, which did not demonstrate a significant treatment benefit, the study will remain open for further follow-up to collect additional survival and safety data. Updated safety and descriptive analyses of overall survival will be performed.

10.5.2 Other secondary efficacy objectives

Not applicable after final PFS analysis

Part 1: Safety run-in and Part 2: Biomarker cohort

The secondary objectives in these parts of the study are to determine the safety and tolerability, evaluate preliminary anti-tumor activity, characterize the pharmacokinetics, and evaluate the prevalence and incidence of immunogenicity of PDR001 in combination with dabrafenib and trametinib.

The incidence and severity of adverse events (AEs) and serious adverse events (SAEs), as well as changes in laboratory values, ECOG PS, vital signs, and liver and cardiac parameters will be summarized. For all safety and tolerability descriptive analyses, the safety set will be used. All listings and tables will be presented by dose cohort (for part 1) and overall (for part 2). Refer to [Section 10.5.3](#) for more details.

To assess preliminary clinical activity, descriptive statistics for PFS, OS, ORR, DCR, and DOR will be summarized by dose cohort (for part 1) and overall (for part 2), using the local review result where applicable. For definitions of these endpoints, refer to [Section 10.4](#), [Section 10.5](#), and the text in [Section 10.5.1](#) for the randomized part of the study. As a supportive analysis, results as per blinded independent central review using RECIST 1.1 and tumor response criteria based on guidelines for immunotherapy will also be presented by dose cohort (for part 1) and overall (for part 2). For details on how censoring will be handled, the same methods described in [Section 10.4.3](#) will be applied.

Refer to [Section 10.5.3](#) for details on the analysis of secondary PK objectives and [Section 10.5.4](#) for details on the analysis of secondary immunogenicity objectives.

Part 3: Double-blind, randomized, placebo-controlled part

Other secondary objectives in this part of the study are to compare the two treatment groups with respect to tumor related efficacy variables (ORR, DOR, and DCR based on RECIST 1.1), safety and tolerability, quality of life, and pharmacokinetics. No multiplicity adjustments are planned for other secondary endpoints.

Overall response rate (ORR) is defined as the proportion of subjects with confirmed best overall response (BOR) of complete response (CR) or partial response (PR), as per local review. ORR will be evaluated according to RECIST 1.1 ([Appendix 1](#)). Complete and partial responses must be confirmed by repeat assessments that should be performed not less than 4 weeks after the criteria for response are first met. ORR based on local review will be calculated based on the FAS. ORR and its 95% confidence interval will be presented by treatment group. The Cochran-Mantel-Haenszel chi-square test, stratified by the randomization stratification factors, will be used to compare ORR between the two treatment groups, at the one-sided 2.5% level of

significance. As a supportive analysis, ORR as per blinded independent central review (using RECIST 1.1 as well as tumor response criteria based on guidelines for immunotherapy) will be presented by treatment group, along with 95% confidence intervals.

Duration of response (DOR) only applies to subjects whose best overall response is complete response (CR) or partial response (PR) based on tumor response data per local review. DOR will be evaluated according to RECIST 1.1 ([Appendix 1](#)). The start date is the date of first documented response of CR or PR (i.e., the start date of response, not the date when response was confirmed), and the end date is defined as the date of the first documented progression or death due to underlying cancer. Subjects continuing without progression or death due to underlying cancer will be censored at the date of their last adequate tumor assessment. DOR based on RECIST 1.1 will be listed and summarized by treatment group for all subjects in the FAS with confirmed BOR of CR or PR, as well as for the subgroup of FAS subjects with confirmed BOR of CR only.

DCR is defined as the proportion of subjects with CR or PR or subjects with stable disease (SD) lasting for a duration of at least 24 weeks as per local review. CR, PR and SD are defined according to RECIST 1.1 (see [Appendix 1](#) for details). DCR will be calculated based on the FAS. DCR and its 95% confidence interval will be presented by treatment group. As a supportive analysis, DCR as per blinded independent central review (using RECIST 1.1 as well as tumor response criteria based on guidelines for immunotherapy) will be presented by treatment group, along with 95% confidence intervals.

In order to characterize the potential for PD-L1 expression to identify subjects with an enhanced response to PDR001, PFS and OS analyses will be performed by PD-L1 subgroup (positive, negative) where a positive status is defined as having $\geq 1\%$ expression and a negative status is defined as having $< 1\%$ expression as determined by immunohistochemistry. Additionally PD-L1 subgroups will also be assessed using $\geq 5\%$ and $\geq 10\%$ as cut-offs for PD-L1 positivity.

Refer to [Section 10.5.3](#) for details on the analysis of secondary safety and tolerability objectives, [Section 10.5.4](#) for secondary PK objectives, [Section 10.5.5](#) for secondary immunogenicity objectives and [Section 10.5.8](#) for secondary quality of life objectives.

10.5.3 Safety objective(s)

10.5.3.1 Analysis set and grouping for the analyses

For all safety analyses, the safety set will be used and data will be presented separately for each part; no pooled safety analyses are planned. For the safety run-in part and biomarker cohort, listings and tables for each part will be presented by dose cohort. For the randomized part, all listings will be presented by treatment group and tables will be presented by treatment group and all subjects.

The overall observation period will be divided into three mutually exclusive segments:

1. pre-treatment period: from day of subject's informed consent to the day before first dose of study medication
2. on-treatment period: from day of first dose of study medication to 30 days after the date of last actual administration of any study medication
3. post-treatment period: starting at day 31 after last dose of study medication.

If dates are incomplete in a way that clear assignment to pre-, on-, or post-treatment period cannot be made, then the respective data will be assigned to the on-treatment period. Additional details to address incomplete AE and/or dosing dates will be addressed in the SAP.

Additional summaries will be displayed to report deaths, all AEs, AEs related to study treatment, all SAEs and SAEs related to study treatment collected up to 150 days after last administration of PDR001/placebo.

Following final PFS analysis, which did not demonstrate a significant treatment benefit, the study will remain open for further follow-up to collect additional survival and safety data. Updated safety and descriptive analyses of overall survival will be performed.

10.5.3.2 Adverse events (AEs)

Summary tables for adverse events (AEs) will include only AEs that started or worsened during the on-treatment period, the **treatment-emergent** AEs.

The incidence of treatment-emergent adverse events (new or worsening from baseline) will be summarized by system organ class and or preferred term, severity (based on CTCAE v4.03 grades), type of adverse event, and relation to study treatment.

Serious adverse events, non-serious adverse events, and adverse events of special interest (AESI; see [Section 8.1.3](#)) during the on-treatment period will be tabulated. The list of AESI's will also include relevant events for dabrafenib and trametinib which will be defined in the SAP.

All deaths (on-treatment and post-treatment) will be summarized.

All AEs, deaths and serious adverse events (including those from the pre and post-treatment periods) will be listed and those starting during the post-treatment period will be flagged.

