8.1 Adverse events

8.1.1 Definitions and reporting

An adverse event is defined as the appearance of (or worsening of any pre-existing) undesirable sign(s), symptom(s), or medical condition(s) that occur after subject's signed informed consent has been obtained.

Subjects whose *BRAF* V600 mutation status is known will sign the main study ICF.

Abnormal laboratory values or test results occurring after informed consent constitute adverse events only if they induce clinical signs or symptoms, are considered clinically significant, require therapy (e.g., hematologic abnormality that requires transfusion or hematological stem cell support), or require changes in study medication(s).

Adverse events that begin or worsen after informed consent should be recorded in the Adverse Events eCRF. Conditions that were already present at the time of informed consent should be recorded in the Medical History page of the subject's CRF. Adverse event monitoring should be continued for at least:

- 150 days following the last dose of PDR001/placebo
- until the start of a new post-treatment antineoplastic medication if sooner than the 150 days mentioned above. If a subject starts a post-treatment antineoplastic therapy, then only adverse events suspected to be related to study treatment should be collected out to 150 days after discontinuation of PDR001/placebo.
- 30 days after the last dose of dabrafenib or 120 days after the last dose of trametinib, if the subject continued the combination partner more than 150 days after the last dose of PDR001/placebo)

Adverse events (including lab abnormalities that constitute AEs) should be described using a diagnosis whenever possible, rather than individual underlying signs and symptoms. When a clear diagnosis cannot be identified, each sign or symptom should be reported as a separate Adverse Event.

Adverse events will be assessed and graded according to the CTCAE v4.03 ([...//ctep.cancer.gov](http://ctep.cancer.gov)).

If CTCAE grading does not exist for an adverse event, the severity of mild, moderate, severe, and life-threatening, death related to the AE corresponding respectively to Grades 1 - 5, will be used. Information about any deaths (related to an Adverse Event or not) will also be collected through a Death form.

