8.1.3 Adverse events of special interest

Adverse events of special interest (AESI) are defined as events (serious or non-serious) which are ones of scientific and medical concern specific to the sponsor's product or program, for which ongoing monitoring and rapid communication by the investigator to the sponsor may be appropriate. Such events may require further investigation in order to characterize and understand them.

Adverse events of special interest are defined on the basis of an ongoing review of the safety data. AESIs are discussed in detail in the Investigator Brochure, and a list of Medical Dictionary for Regulatory Activities (MedDRA) preferred terms to flag as AESI's will be included in the SAP.

AESI for dabrafenib include:

- Hypersensitivity
- Pyrexia
- cuSCC including keratoacanthoma
- Non-cutaneous treatment emergent malignancies
- New primary melanoma
- pre-renal and intrinsic renal failure
- Uveitis
- Hyperglycemia
- Pancreatitis
- Neutropenia (in combination with trametinib)

AESI for trametinib include:

- Skin related toxicities
- Ocular events
- Cardiac related events
- Hepatic disorders
- Pneumonitis/interstitial lung disease
- Bleeding events
- Diarrhea
- Hypertension
- Edema
- Hypersensitivity
- Deep vein thrombosis/pulmonary embolism

AESI for PDR001 include:

- Endocrinopathies
- Pneumonitis
- Colitis
- Hepatitis

- Nephritis
- Encephalitis
- Rash
- Infusion reaction
- Other immune disorders

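### The grouped AESI tables stop at the on-treatment window, and the 150-day safety summaries do not name AESIs

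*Protocol*

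**What the plan says.** Four parts of the protocol bear on this.

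- **Analysis window.** Section 10.5.3.1 splits observation into three periods. The middle one is the "on-treatment period: from day of first dose of study medication to 30 days after the date of last actual administration of any study medication".
- **What is tabulated in it.** Section 10.5.3.2 opens with a general rule: "Summary tables for adverse events (AEs) will include only AEs that started or worsened during the on-treatment period". It then says that SAEs, non-serious AEs and AESIs "during the on-treatment period will be tabulated". All AEs, including those from the post-treatment period, are to be listed, with post-treatment starts flagged.
- **The longer summaries.** Section 10.5.3.1 also promises additional summaries of "deaths, all AEs, AEs related to study treatment, all SAEs and SAEs related to study treatment collected up to 150 days" after the last PDR001/placebo administration. AESIs are not in that list.
- **Collection.** Section 8.1.1 keeps AE monitoring open for at least "150 days following the last dose of PDR001/placebo". Once a new antineoplastic therapy starts, only events suspected to be related are collected up to that day.

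Section 8.1.3 has a list headed "AESI for PDR001 include". It is mostly immune-mediated: colitis, hepatitis, pneumonitis and endocrinopathies are among its entries. The same section leaves the preferred terms that make up the AESIs to the SAP.

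**The concern.** The protocol lengthens the reporting window for AEs in general but not for the category that it singles out as being of special concern. AESIs are reported as groups of preferred terms, and the quantity of interest is the number of patients with at least one term in a group. As written, that number is planned only for the on-treatment window.

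A patient whose first hepatitis-type event starts well after the last dose, but inside the 150-day collection period, would be in the database and in the 150-day AE output. The same patient would be missing from the grouped hepatitis count. Immune toxicity is a main safety question when PDR001 is added to dabrafenib and trametinib, so the grouped counts are what a reader would look for. Safety follow-up continues after the final PFS analysis and updated safety analyses are promised, so a change would still affect what is reported.

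**Working it through.** The plan gives no numerical figure on this point to reproduce. The check compares the windows and then asks whether the 150-day summaries can stand in for the missing table.

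**Inputs**
- End of the on-treatment period: 30 days after the last dose of *any* study drug (Section 10.5.3.1).
- End of AE collection and of the added summaries: 150 days after the last PDR001/placebo dose (Sections 8.1.1 and 10.5.3.1).
- Let g be the number of days by which the last dose of dabrafenib or trametinib, whichever is later, follows the last dose of PDR001/placebo.

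**Days of the 150-day window outside the AESI tables** = max(0, 150 − (30 + g)).

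| g (days) | Calculation | Days outside | Share of 150 |
|---|---|---|---|
| 0 | 150 − 30 | 120 | 80% |
| 30 | 150 − 60 | 90 | 60% |
| 60 | 150 − 90 | 60 | 40% |
| 90 | 150 − 120 | 30 | 20% |
| 120 or more | 150 − 150 or less | 0 | 0% |

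The figure of 120 days is therefore the maximum. It applies when all components stop together.

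**Can the 150-day AE summaries supply the grouped count?** Every colitis or hepatitis collected by day 150 is an AE, so it enters the all-AE summary and, where applicable, the related-AE and SAE summaries. Section 10.5.3.1 does not fix the layout of these summaries. If they are laid out by preferred term, the rows do not add up to a group count, because a patient with two terms in one group appears in two rows. The group count is then known only to lie between the largest row and the sum of the rows. Listings contain the data but give no rate by arm.

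**Is this left to the SAP?** The term list is. The window is not: Section 10.5.3.2 states it.

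**A further inconsistency.** Section 10.5.3.2 restricts AE summary tables to the on-treatment period with the word *only*, while Section 10.5.3.1 commits to AE summaries up to day 150. Read literally, the two cannot both hold.

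**The case against.** The case for leaving the text alone has real force.

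- **Nothing is lost from the report.** A reader might infer that late immune events go unreported. The documents do not support this: the 150-day summaries cover all AEs, Part 3 tables are by treatment group, and post-treatment events are listed and flagged. Only the grouped view is missing. This stands, and it limits the point.
- **The 30-day rule is an ordinary treatment-emergent convention.** It applies equally to SAEs, non-serious AEs and AESIs. True, but for AEs and SAEs the protocol adds the longer window, and for AESIs it does not.
- **The SAP could add the table.** It could, and nothing in the protocol forbids grouping within the 150-day output. The protocol nevertheless sets the shorter window and omits AESIs from the longer list, so it is reasonable to ask for the text to be changed.
- **The clock runs from the last dose of any drug.** This stands. For patients who stay on dabrafenib or trametinib after PDR001, the gap is smaller or absent.
- **Direction of bias.** A reader might infer that the omission makes PDR001 look safer than it is, because placebo patients would have hardly any late immune events. The protocol does not show this. Its AESI lists overlap: trametinib has hepatic disorders, pneumonitis/interstitial lung disease and skin toxicities of its own, so control patients also contribute. After new therapy only suspected events are collected, so days 31 to 150 are incompletely observed in a way that may differ by arm.

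**Conclusion.** The point holds in a limited form. The grouped AESI incidence planned in Section 10.5.3.2 omits events that start more than 30 days after the last study drug, although such events are collected and appear elsewhere in the output. The uncovered stretch is at most 120 of 150 days (80%), reached when all components stop together, and it falls to zero when dabrafenib or trametinib continues for at least 120 further days.

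This may understate grouped immune-toxicity incidence. It is tempting to turn it into a number of missing patients. That would need the share of patients with an immune AESI, the share whose first such event falls after the window, and the distribution of g. The protocol gives none of these, so neither a count nor a between-arm effect can be stated. No hypothesis test, stopping rule or primary estimate is touched. The severity is minor.

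**What to change.** In Section 10.5.3.1, add AESIs to the list of summaries up to 150 days after the last PDR001/placebo dose: overall, by AESI group and by grade, by arm. Keep the on-treatment AESI table. In Section 10.5.3.2, reword the *only* sentence so that it allows the 150-day summaries.

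The cost is one more table from data already collected. It needs a footnote saying that after the start of a new antineoplastic therapy only events suspected to be related are collected. Without that note a reader could take the later part of the window as fully ascertained.
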